10.4. Dispensing and Storage

The trial drug products supplied by the sponsor is to be dispensed exclusively to patients randomized in this clinical trial according to the instructions of this protocol and the pharmacy manual/trial materials manual (TMM). The investigator is responsible for dispensing the trial drug product according to the dosage scheme. Trial drug products will be allocated using an interactive automated web response system (IWRS), according to Section 10.5.

Dasiglucagon and placebo for dasiglucagon injection must be stored at 2–8°C in a refrigerator.

The investigator must ensure the availability of proper storage conditions. All trial drug products provided for this trial will be stored at the trial site in a secure area with restricted access.

The temperature should be monitored by recording the actual, minimum, and maximum temperatures using a calibrated thermometer or thermocouple, or by continuous recording using a qualified temperature monitoring system. The temperature should be evaluated and documented at least on working days on a temperature log. This log must be included in the Investigator Site File (ISF) upon trial termination.

The investigator must contact the clinical research associate (CRA) in case of temperature deviations outside the acceptable range.

Please see the pharmacy manual/TMM for additional information on handling of the trial drug.

The investigator must maintain adequate records showing the receipt, dispensing, return, or other disposition of the trial drug, including the date, quantity, batch or code number, and identification of patients (patient number) who received the trial drug. The investigator will not supply the trial drug to any person except subinvestigators, designated trial personnel, and patients in this trial. The trial drug may not be relabeled or reassigned for use by other patients. If any of the trial drug is not dispensed, is lost, stolen, spilled, unusable, or is received in a damaged container, this information must be documented and reported to the sponsor and the appropriate regulatory agencies as required.

10.5. Method of Assigning Patients to Treatment Groups

For Part 1, patients will be randomly assigned 1:1 in a double-blind fashion to 1 of 2 sequences:

- Dasiglucagon 4 mg/mL for 48 hours, followed by placebo for dasiglucagon for 48 hours, or
- Placebo for dasiglucagon for 48 hours, followed by dasiglucagon 4 mg/mL for 48 hours.

Randomization will be performed using a block randomization scheme stratified by region (US/non-US). The randomization scheme will be generated prior to the initiation of the trial by

an independent statistician/programmer who will not be a member of the trial team; investigators will not be aware of the block size of the randomization scheme.

Patients will be randomly assigned to a trial treatment sequence using an IWRS that has been validated for the intended use under the International Society of Pharmaceutical Engineers Good automated manufacturing practice guidelines, 21CFR Part 11 (FDA regulation for Electronic Records and Electronic Signatures), and the ICH Guidance E6 for Industry on Good Clinical Practice.

After completing Part 1, patients will continue in Part 2 to receive active treatment for a maximum of 21 days.

10.6. Blinding and Unblinding Treatment Assignment

Trial personnel will endeavor to safeguard the integrity of the trial blind to minimize bias in the conduct of the trial. Treatment unblinding is discouraged if knowledge of the treatment assignment will not materially change the planned management of a medical emergency. Unblinding will be permitted in a medical emergency that requires immediate knowledge of the patient's treatment assignment.

For emergency unblinding, the investigator will use the measures provided through the IWRS. Unblinding should be discussed in advance with the medical monitor if possible. If the investigator is not able to discuss treatment unblinding in advance, then he or she must notify the medical monitor as soon as possible about the unblinding incident without revealing the patient's treatment assignment.

The investigator or designee must record the date and reason for unblinding on the appropriate eCRF page for that patient.

10.7. Selection of Doses in the Trial

Both the starting dose and the maximum allowed doses are based on experience with marketed glucagon products in this patient population.¹¹

At present, no pediatric PK data are available for dasiglucagon. However, an approximate estimation of expected drug concentration in a 3 kg patient has been made by extrapolation of a previously made PK model for pediatric patients with weights between 25 and 45 kg.¹⁷

In this trial, dasiglucagon will be titrated to meet the needs of the individual patient on the basis of PD effects in regards to efficacy and tolerability, and it is expected that the majority of patients will be adequately treated with a dasiglucagon infusion rate of approximately 20 to 40 µg/hr. The up-titration will stop when IV glucose is completely weaned, if undesirable side effects arise, or when no additional PD effects are observed as the dasiglucagon infusion rate is increased.

Based on the current PK/PD model, the predicted plasma concentration is expected to result in a medium PD response at the lowest dose level and be approaching maximum effect at the highest dose level. The PD response of patients will be monitored closely in this trial, and the appropriateness of the applied titration algorithm will be evaluated.

Although the PK of dasiglucagon has been shown to be dose-proportional in adults and in all toxicologically tested species over a wide range of doses, limited PK sampling at each dose level is planned based on the limited available blood volume in this population.

10.8. Selection of Timing of Dose for Each Patient

Dosing details are provided in Section [10.2](#).

10.9. Dose Adjustment Criteria

Dose adjustment criteria are presented in Section [10.2](#).

10.10. Treatment Compliance

Compliance data will be collected. Infusion details will be recorded in the patient's eCRF and drug accountability will be performed as detailed in the pharmacy manual/TMM.

10.11. Permitted and Prohibited Therapies

All concomitant medications used (including over-the-counter medications and herbal supplements) will be recorded in the source document and on the appropriate eCRF.

Caution is advised when beta-blockers, indomethacin, anticholinergic drugs, and warfarin are prescribed due to reports of interaction with marketed glucagon products.

10.11.1. Permitted Therapies

Regarding diazoxide, patients entering the trial either:

- Have tried diazoxide, but discontinued due to lack of efficacy. Minimum of 6 days' washout is required prior to randomization.
- Have tried diazoxide, but discontinued due to adverse events, or family choice, even if efficacy was established. Minimum of 6 days' washout is required prior to randomization.
- Have initiated diazoxide prior to screening, and continue on the treatment. Diazoxide dose should remain stable during Part 1 of the trial. Diazoxide should not be initiated during screening.
- Have never tried diazoxide. Diazoxide should not be initiated during screening or Part 1 of the trial.

Prior use of octreotide is allowed after a minimum 48-hour washout prior to randomization. Washout is required to eliminate the effect of octreotide during Part 1, where adjustment of GIR has to follow the protocol-defined PG-driven algorithm ([Table 1](#)) and the primary endpoint on mean GIR is assessed.

Somatostatin analogs and/or diazoxide can be introduced during Part 2 if needed, at the investigator's discretion, when the maximal limit of dasiglucagon (70 µg/hr) has been reached or if further up-titration is not possible due to undesirable side effects.

Addition of other CHI-specific treatments (e.g., sirolimus/mTOR inhibitors) during Part 2 need to be discussed with the medical monitor.

10.11.2. Prohibited Therapies

The following therapies are prohibited:

During the entire trial:

- Systemic corticosteroids, e.g., hydrocortisone >20 mg/m² body surface area or equivalent within 5 days before screening.
- Anti-inflammatory biological agents or other immune-modulating agents.

- Other investigational agents.
- Marketed glucagon products within the last 24 hours prior to randomization and throughout the trial unless necessary for rescue therapy in case of severe hypoglycemia, as per local standard of care.
- Prescription or non-prescription medications known to cause QT prolongation.

During Screening and Part 1:

- Somatostatin analogs and sirolimus (mTOR inhibitors). No new CHI treatment is to be initiated during screening and Part 1. Octreotide is allowed in the screening period if discontinued at least 48 hours before randomization.

During Part 2 and follow-up:

- Initiation of somatostatin analogs, diazoxide and sirolimus (mTOR inhibitors) unless the maximum dose level of dasiglucagon (70 µg/hr) has been reached or further dasiglucagon up-titration is not possible due to undesirable side effects.

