- IV GIR has not decreased despite 2 sequential dose increments of trial drug (in this situation, the dose of trial drug should be maintained until the IV GIR can be further decreased or until crossover or the end of Part 1), or
- The maximum dose of 70 µg/hr is reached, or
- AEs emerge that are considered to be related to dasiglucagon (e.g., nausea/change in feeding pattern or increased vomiting) that are limiting further dose escalation

The 2-hour dose-adjustment interval will allow drug plasma levels to approach steady-state before the dose is further increased. The cumulative dose will not exceed 1.26 mg over the first 24 hours and 1.68 mg for each of the subsequent 24-hour periods.

At the time of crossover from the first 48-hour period to the second 48-hour period, the trial drug will again be titrated from the starting dose of 10 µg/hr, and IV GIR will be set to the rate obtained at the end of the run-in period and titrated accordingly.

Part 2 (Open label)

After Part 1, patients will continue in open-label Part 2 to receive dasiglucagon for a further 21 days. Since treatment allocation during Part 1 remains blinded, all patients are required to initiate dasiglucagon dosing at 10 µg/hr in Part 2, while IV GIR should be started at the rate obtained at the end of the run-in period.

During Part 2, the dasiglucagon dose, the amount and route of administration of carbohydrates (IV GIR, parenteral nutrition, gastric carbohydrate infusions, and carbohydrates from oral feeds) can be adjusted at the discretion of the investigator. The PG should be monitored at least hourly to adjust the IV GIR as appropriate and to avoid hypoglycemia. Additional concomitant medications, including somatostatin analogs and/or sirolimus/mTOR inhibitors, may be introduced at the investigator's discretion if the maximum dose level of dasiglucagon (70 µg/hr) has been reached or if further up-titration is not possible due to undesirable side effects.

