Adjustment of total carbohydrate administered (IV glucose, parenteral nutrition, carbohydrate infusions, and carbohydrates from oral feeds) should continue throughout this period according to local practice to maintain PG levels in the range of 70 mg/dL to 120 mg/dL (3.9-6.7 mmol/L). The aim will be to obtain stable glucose levels with minimum rescue/hypoglycemia-preventative carbohydrates administered by invasive routes, and to encourage/optimize oral feeds, and achieve weaning off IV glucose. Regardless of their discharge status, all patients will be offered the opportunity to participate in the long-term safety extension trial (ZP4207-17106), providing the investigator attests to the positive benefit-risk balance of continued dasiglucagon treatment.

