10.13. Treatment After End of Trial

On Day 25, the End of Treatment Visit will take place. Based on the investigator's confirmation of continued positive benefit-risk balance, patients will be offered the opportunity to enter the long-term extension trial (Trial ZP4207-17106) to continue dasiglucagon treatment. Patients who do not enter the long-term extension trial will have a Follow-up Visit 28 days after their last dose of trial drug and return to standard of care as per investigator discretion. No further treatment with dasiglucagon will be offered.

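### Section 10.11.2 carries a dasiglucagon-titration condition for starting other CHI drugs into follow-up, when a child no longer receives dasiglucagon and cannot newly meet it

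*Protocol*

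**What the plan says.** The wording below is the same in versions 13.0 and 14.0.

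- **Section 10.11.2, Prohibited Therapies.** Under the heading "During Part 2 and follow-up" the protocol bars "Initiation of somatostatin analogs, diazoxide and sirolimus (mTOR inhibitors) unless the maximum dose level of dasiglucagon" has been reached. That level is 70 µg/hr. The only other release is that up-titration cannot continue because of side effects.
- **Section 10.13, Treatment After End of Trial.** Children who do not enter the extension have a Follow-up Visit 28 days after the last dose and "return to standard of care as per investigator discretion". The section adds: "No further treatment with dasiglucagon will be offered".
- **Section 18.1, Schedule of Events, footnote a.** The Follow-up Visit is only for children who do not enter the extension.
- **Section 10.11.1, Permitted Therapies.** The same titration condition is stated for Part 2 only.
- **Section 9.5, Rescue Criteria.** In Part 2, any CHI treatment may be started. No titration condition is attached.
- **Section 6.2.** Diazoxide is first-line treatment and a somatostatin analog second-line.

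Sections 10.11.2 and 10.13 do not refer to each other.

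**The concern.** A condition based on dasiglucagon titration makes sense while the child is being titrated. It does not once the drug has been stopped for good. Carried into follow-up, it can no longer be newly satisfied, yet it still controls access to the drugs that Section 6.2 names as first- and second-line treatment. Section 10.11.2 also limits marketed glucagon throughout the trial to rescue in severe hypoglycemia.

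At stake are clear instructions for treating infants who needed continuous IV glucose at entry, and consistent classification of deviations. One site could start diazoxide under Section 10.13. Another could hold back, or record a deviation, under Section 10.11.2.

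**Working it through.** **1. Is follow-up inside the trial?** Section 11.1 gives screening 28 days, Part 1 96 hours (4 days), Part 2 21 days, and follow-up 28 days after the last dose.

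- Trial duration: 28 + 4 + 21 + 28 = 81 days, the stated maximum.
- Treatment: 4 + 21 = 25 days, the stated maximum.
- Follow-up Visit: 25 + 28 = Day 53, as in the Schedule of Events.

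For a child treated to Day 25, the 28 days to Day 53 are in-trial days without dasiglucagon, and Section 10.11.2 applies to them.

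**2. Who is in follow-up?** Footnote a and Section 10.13 describe the same children: those outside the extension, with no further dasiglucagon. No titration takes place, so neither exception can be newly met.

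**3. Could an exception have been met earlier?** Yes, in either part. The condition asks whether 70 µg/hr has been reached and does not limit this to Part 2. In Part 1 (Section 10.2) the dose starts at 10 µg/hr and rises by 10 every 2 hours, so unstopped escalation reaches 70 µg/hr at hour 12. First-day dose: 2 × (10 + 20 + 30 + 40 + 50 + 60) + 12 × 70 = 420 + 840 = 1260 µg, which reproduces the stated 1.26 mg cap. Part 1 allocation stays blinded, so an investigator may not know whether a 70 µg/hr rate was active drug. A child taken to 70 µg/hr in both periods must have reached it on dasiglucagon.

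**4. Can a child miss both exceptions?** Yes. Section 10.7 states that "it is expected that the majority of patients will be adequately treated with a dasiglucagon infusion rate of approximately" 20 to 40 µg/hr, which is 20/70 = 29% to 40/70 = 57% of the releasing dose. It also states: "The up-titration will stop when IV glucose is completely weaned, if undesirable side effects arise, or when no additional PD effects are observed". Of those three reasons only side effects match an exception. In Part 2 the dose "can be adjusted at the discretion of the investigator", so nothing forces it up to 70 µg/hr.

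**5. What do the two sections require together?**

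| Reading of Section 10.13 | Result for a child who met neither exception |
|---|---|
| Standard of care from Day 25 | Section 10.13 permits starting the drug and Section 10.11.2 forbids it |
| Standard of care only after the Follow-up Visit | No conflict, but these drugs cannot be newly started for 28 days |

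**6. How many children?** The documents give no figure. As an illustration only, assume that 10% to 30% of the 12 do not enter the extension and that 25% to 75% of those met neither exception. Then 12 × 0.10 × 0.25 = 0.3 and 12 × 0.30 × 0.75 = 2.7 children. Both inputs are assumptions, and the child must also need a newly started drug, which lowers the count further.

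**The case against.** The best counter-argument is that the sections apply in sequence. Section 10.13 is titled for treatment after the trial, and Section 11.2.3.1 calls Visit 8 the end of trial visit. Section 10.13 also mentions the Follow-up Visit before the return to standard of care. On that reading Section 10.11.2 governs to Day 53 and Section 10.13 afterwards. The reading is possible, so a reader who infers a certain contradiction goes further than the text. It does not rescue the rule, because it leaves the 28-day restriction in step 5.

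A reader might also infer that every child who stayed below 70 µg/hr in Part 2 is caught. Step 3 shows why not: the exception may have been met in Part 1.

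Nor does the text leave children without options. The ban covers only newly started drugs. Ongoing diazoxide, anything begun by the end of Part 2 under Section 9.5, IV or enteral glucose, surgery and rescue glucagon all remain. Section 10.13 is the more specific rule and many investigators would follow it. Section 20.4.4, which requires even medically justifiable deviations to be reported, is in version 14.0 only. It permits deviation in an emergency, and its examples do not mention concomitant medication. All of this stands and makes the point smaller. None of it gives the titration condition a purpose in follow-up.

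**Conclusion.** The rule as written gives the wrong result in follow-up under either reading of Section 10.13. That Section 10.11.1 states the condition for Part 2 only suggests the extension to follow-up was not intended.

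The point is minor. The number affected is unknown and probably small. It might be inferred from the expected 20 to 40 µg/hr that most of the 12 are exposed. The documents do not support that: those are children expected to be adequately treated, so they are likely to enter the extension, which is offered "providing the investigator attests to the positive benefit-risk balance of continued dasiglucagon treatment". Children kept out because of side effects may already meet the second exception. No efficacy analysis is affected, since the Part 2 endpoints cover Days 5 to 25. The consequence is for patient care and deviation classification. The conclusion rests on the text alone and not on the illustrative count.

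**What to change.** In Section 10.11.2 of versions 13.0 and 14.0:

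1. Replace the heading "During Part 2 and follow-up" with: *During Part 2, while the patient is receiving dasiglucagon:*
2. Add below the bullet: *After dasiglucagon has been stopped in Part 2 or at the End of Treatment Visit, CHI treatment is at the investigator's discretion (Section 10.13); the prohibitions listed under During the entire trial still apply.*

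This also covers a child who stops dasiglucagon early in Part 2 but stays in the trial under Section 9.4. The Screening and Part 1 prohibitions stay under their own heading and need no mention here, so primary-endpoint data remain protected. The limit on marketed glucagon is unchanged. Exclusion criterion 7 lists sirolimus beside other immune-modulating agents, so the sponsor should state whether the whole-trial ban on that class covers it.

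Cost: one heading and one sentence in two versions, by formal amendment (Section 14.8), which can be combined with the next one. There is a small downside. CHI drugs newly started in follow-up must be recorded as concomitant medication, which the Schedule of Events already collects at Day 53. They must also be considered when interpreting follow-up adverse events, laboratory tests and echocardiograms.

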10.12. Discharge of Patients for Home Treatment

Patients can be discharged during Part 2 to complete the treatment at home as soon as IV GIR has been weaned off and local site criteria for discharge are met. Discharge for home treatment is contingent on the parent(s)/guardian being capable of taking care of the administration of investigative product via pump at home, can use SMPG and CGM device, and are able to attend planned assessment visits at the hospital.

Before discharge of patients from hospital care, the investigator will ensure:

- Appropriate training of patient's parent(s)/guardian in the use of dasiglucagon in the Accu-Chek Spirit Combo pump based on the training material provided. The first pump infusion set change should be performed at the hospital
- Parent(s)/guardian are trained appropriately on the handling of CGM device
- Parent(s)/guardian are trained appropriately on how to perform SMPG measurements and how to complete the diary. They will check their child's SMPG at least 3 times daily (preferably before main meals) and in case of suspected hypoglycemia
- Parent(s)/guardian are instructed not to change the dose of trial drug without prior consultation with the investigator
- Parent(s)/guardian are instructed how to recognize and handle signs of hypoglycemia
- Parent(s)/guardian are instructed to call the investigator/site staff in case of questions

Patients who are discharged from hospital before Day 25 will be contacted by the investigator by telephone the day after discharge. The investigator will ask the parent(s)/guardian if they have any questions about the trial procedures and if their child has experienced any AEs.

10.13. Treatment After End of Trial

On Day 25, the End of Treatment Visit will take place. Based on the investigator's confirmation of continued positive benefit-risk balance, patients will be offered the opportunity to enter the long-term extension trial (Trial ZP4207-17106) to continue dasiglucagon treatment. Patients who do not enter the long-term extension trial will have a Follow-up Visit 28 days after their last dose of trial drug and return to standard of care as per investigator discretion. No further treatment with dasiglucagon will be offered.

11. TRIAL PROCEDURES

Patients' parent(s)/guardian (according to local law) must provide written informed consent before any trial-related procedures are initiated, including the cessation of prohibited concomitant therapy.

For the timing of assessments and procedures throughout the trial, refer to the Schedule of Events (Section 18.1). Throughout the trial, trial personnel should make every reasonable effort to follow the timing of assessments and procedures in Section 18.1 for each patient. If a patient misses a trial visit for any reason, it should be rescheduled as soon as possible.

11.1. Trial Duration

The sequence and maximum duration of the trial periods will be as follows:

1. Screening Period: up to 28 days, including a minimum 24-hour run-in period
2. Part 1 (2x48-hour period: double-blind, randomized, placebo-controlled): 96 hours
3. Part 2 (Open-label Active Treatment Period): 21 days
4. Follow-up Period: Patients who do not enter the extension trial will have a Follow-up Visit 28 days after their last dose of trial drug

The maximum trial duration for each patient is 81 days. The maximum treatment duration for each patient is 25 days.

